8.4.2.2 EVENTS THAT OCCUR AFTER STUDY DRUG INITIATION

After initiation of study drug, SAEs and AESIs will be reported after Follow-up (12 to 14 days after the final dose of study drug). Investigators should record all case details that can be gathered immediately on a paper Clinical Trial SAE/AESI Reporting Form. The completed paper Clinical Trial SAE/AESI Reporting Form should be completed and submitted to the Sponsor (via Covance PSS) immediately (i.e., no more than 24 hours after learning of the event), either by faxing or by scanning and emailing the form using the fax number or email address provided in [Section 8.4.2.1](#). All information will also need to be entered into the AE eCRF.

Relevant follow-up information should be submitted to Covance PSS on an updated paper Clinical Trial SAE/AESI Reporting Form as soon as it becomes available and/or upon request. Any updates to the paper Clinical Trial SAE/AESI Reporting Form must also be updated in electronic data capture (EDC) on the AE eCRF.

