Potential subjects will be screened to assess their eligibility to enter the study within 34 days (Days -35 to -2) prior to dosing on Period 1 Day 1. Replacement subjects will not be enrolled. For all subjects, routine Screening procedures, as outlined in Section 5.1, will be performed.

Eligible subjects will be admitted to the study site on the day prior to GDC-9545 dosing (Check-in [Day -1]) of Period 1 to collect baseline data and familiarize the subjects with study procedures that will be used during the rest of the study. On Period 1 Day 1, subjects will be randomly assigned to one of six possible treatment sequences and the first dose of GDC-9545 in the assigned sequence will be administered in the morning. The washout period between doses will be a minimum of 10 days based on the GDC-9545 geometric mean apparent terminal elimination half-life ($t_{1/2}$) of approximately 40 hours.

Subjects will be confined at the study site from the time of Check-in (Day -1) until Clinic Discharge on Day 8 of each period. Subjects will return to the study site for a Follow-up visit 12 to 14 days after the last dose of GDC-9545. A detailed list of assessments during confinement is included in [Table 7-1](#).

In this study design, physical examinations, 12-lead ECGs, vital signs, How do you feel? (HDYF?) inquiries, clinical laboratory evaluations ([Appendix A](#)), and PK sampling will be performed at Screening, at specified times during the study, and/or at Follow-up/Early Termination (ET; for specific timepoints and details on each study variable, refer to [Section 7](#)). After informed consent has been obtained but prior to initiation of study drug administration (Period 1 Day 1), only SAEs caused by protocol-mandated interventions will be reported. After initiation of study drug administration on Period 1 Day 1, all AEs, whether volunteered, elicited, or noted upon physical examination, will be recorded throughout the study (i.e., from Period 1 Day 1 until Follow-up/ET). The Sponsor should be notified if the Investigator becomes aware of any SAE that occurs after the follow-up period (defined as 12 to 14 days after the last dose of GDC-9545) if the event is believed to be related to prior study drug treatment.

A schedule of activities is presented in [Table 7-1](#).

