8.1.2 SERIOUS ADVERSE EVENTS (IMMEDIATELY REPORTABLE TO THE SPONSOR)

An SAE is any AE that meets any of the following criteria:

- Is fatal (i.e., the AE actually causes or leads to death)
- Is life-threatening (i.e., the AE, in the view of the Investigator, places the subject at immediate risk of death); this does not include any AE that had it occurred in a more severe form or was allowed to continue might have caused death
- Requires or prolongs inpatient hospitalization
- Results in persistent or significant disability/incapacity (i.e., the AE results in substantial disruption of the subject's ability to conduct normal life functions)
- Is a congenital anomaly/birth defect in a neonate/infant born to a mother exposed to study drug
- Is a significant medical event in the Investigator's judgment (e.g., may jeopardize the subject or may require medical/surgical intervention to prevent one of the outcomes listed above).

All AEs that do not meet any of the criteria for serious should be regarded as non-serious AEs.

The terms “severe” and “serious” are not synonymous. Severity refers to the intensity of an AE (e.g., rated as mild, moderate, or severe, according to National Cancer Institute Common Terminology Criteria for Adverse Events [NCI CTCAE]); the event itself may be of relatively minor medical significance (such as severe headache) without any further findings. An event should be considered “serious” only if it meets the regulatory criteria outlined in the above-mentioned paragraph outlining seriousness criteria.

Seriousness (not severity) serves as the guide for defining regulatory reporting obligations.

Severity and seriousness need to be independently assessed for each AE recorded on the eCRF.

Serious AEs are required to be reported by the Investigator to the Sponsor via Covance Patient Safety Solutions (PSS) immediately (i.e., no more than 24 hours after learning of the event; see [Section 8.4.2](#) for reporting instructions).

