8.1.3 ADVERSE EVENTS OF SPECIAL INTEREST (IMMEDIATELY REPORTABLE TO THE SPONSOR)

Adverse events of special interest are required to be reported by the Investigator to the Sponsor via Covance PSS immediately (i.e., no more than 24 hours after learning of the event; see [Section 8.4.2](#) for reporting instructions). Adverse events of special interest for this study are as follows:

- Cases of potential drug-induced liver injury that include an elevated ALT or AST in combination with either an elevated bilirubin or clinical jaundice, as defined by Hy’s Law (see [Section 8.3.1.6](#))
- Suspected transmission of an infectious agent by the study drug as defined below:
 - Any organism, virus, or infectious particle (e.g., prion protein transmitting transmissible spongiform encephalopathy), pathogenic or non-pathogenic, is considered an infectious agent. A transmission of an infectious agent may be suspected from clinical symptoms or laboratory findings that indicate an infection in a subject exposed to a medicinal product. The term applies only when a contamination of the study drug is suspected
- Grade ≥ 3 nausea/vomiting/diarrhea
- Grade ≥ 2 thromboembolic events (pulmonary embolism, deep vein thrombosis, and embolism)
- Grade ≥ 3 renal failure (including acute kidney injury or other similar medical concepts)
- Grade ≥ 3 hepatitis or elevation in ALT or AST
- Grade ≥ 2 vaginal or uterine hemorrhage

- Grade ≥ 2 bradycardia
- Any grade of endometrial cancer.

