8.2.1 ADVERSE EVENT REPORTING PERIOD

Investigators will seek information on AEs at each subject contact. All AEs, whether reported by the subject or noted by study personnel, will be recorded in the subject's medical record and on the AE eCRF.

After informed consent has been obtained but prior to initiation of study drug administration, only SAEs caused by a protocol-mandated intervention (e.g., discontinuation of medications) will be reported (see [Section 8.4.2](#) for instructions for reporting SAEs). After initiation of study drug administration, all AEs will be recorded throughout the study until Follow-up (defined as 12 to 14 days after the last dose of GDC-9545). The Sponsor should be notified if the Investigator becomes aware of any SAE that occurs after the follow-up period (defined as 12 to 14 days after the last dose of GDC-9545) if the event is believed to be related to prior study drug treatment.

Instructions for reporting AEs that occur after the AE reporting period are provided in [Section 8.6](#).

The Investigator is not required to actively monitor subjects after the study has ended or for AEs after the end of the AE reporting period (defined as until Follow-up, 12 to 14 days after the final dose of study drug). However, the Sponsor should be notified if the Investigator becomes aware of any death, other SAEs, or AESIs occurring after the end of the AE reporting period that are believed to be related to prior study drug treatment. The Sponsor should also be notified if the Investigator becomes aware of the development of cancer or a congenital anomaly/birth defect in a subsequently conceived offspring of a female subject exposed to study drug.

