8.4 IMMEDIATE REPORTING REQUIREMENTS FROM INVESTIGATOR TO SPONSOR

Certain events require immediate reporting to allow the Sponsor to take appropriate measures to address potential new risks in a clinical trial. The Investigator must report such events to the Sponsor immediately via Covance PSS; under no circumstances should reporting take place more than 24 hours after the Investigator learns of the event. The following is a list of events that the Investigator must report to the Sponsor within 24 hours (see [Section 8.4.2](#)) after learning of the event, regardless of relationship to study drug:

- SAEs (see [Section 8.4.2](#) for further details)
- AESIs (see [Section 8.1.3](#) for further details)
- Pregnancies (see [Section 8.4.2.3](#) for further details).

For SAEs and AESIs, the Investigator must report new significant follow-up information for these events to the Sponsor immediately via Covance PSS (i.e., no more than 24 hours after becoming aware of the information). New significant information includes the following:

- New signs or symptoms or a change in the diagnosis
- Significant new diagnostic test results
- Change in causality based on new information
- Change in the event's outcome, including recovery
- Additional narrative information on the clinical course of the event.

Investigators must also comply with local requirements for reporting SAEs to the local health authority and IRB/EC.

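### Protocol 8.4.2.2 opens by placing SAE and AESI reporting after Follow-up, against its own 24-hour deadline and a reporting period that ends at Follow-up

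*Protocol*

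**What the plan says.** Section 8.4.2 has one subsection for events before study drug (8.4.2.1) and one for events after it starts (8.4.2.2). The second opens: "After initiation of study drug, SAEs and AESIs will be reported after Follow-up (12 to 14 days after the final dose of study drug"). Later in the same paragraph the completed paper form is to be "submitted to the Sponsor (via Covance PSS) immediately (i.e., no more than 24 hours after learning of the event").

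Other sections deal with the same reports:

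- Section 8.4, the parent section: "under no circumstances should reporting take place more than 24 hours after the Investigator learns of the event".
- Section 8.1.2 requires SAEs to be reported "to the Sponsor via Covance Patient Safety Solutions (PSS) immediately (i.e., no more than 24 hours after learning of the event").
- Section 8.1.3: "Adverse events of special interest are required to be reported by the Investigator to the Sponsor via Covance PSS immediately", with the same 24-hour limit.
- Section 4.1 says that adverse events "will be recorded throughout the study (i.e., from Period 1 Day 1 until Follow-up/ET").
- Section 8.2.1: "After initiation of study drug administration, all AEs will be recorded throughout the study until Follow-up". It also defines the adverse event reporting period as ending at Follow-up, 12 to 14 days after the final dose, and Section 8.6 repeats that definition.
- For the time after Follow-up, Section 8.2.1 asks the Investigator to notify the Sponsor of deaths, other SAEs or AESIs "occurring after the end of the AE reporting period that are believed to be related to prior study drug treatment". Section 8.6 applies the same relatedness condition to SAEs and gives a separate reporting route.

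**The concern.** A site reading 8.4.2.2 meets a rule that places SAE and AESI reporting after the Follow-up visit, and then a 24-hour deadline in the same paragraph. Both cannot hold for an event that occurs during the dosing periods or before Follow-up, which is when nearly all reportable events in this study would be expected.

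The location adds to the concern. Sections 8.1.2, 8.1.3, 8.3.1 and 8.4 all refer the Investigator to 8.4.2 for reporting instructions. Section 8.4.2.1 states the window before study drug, so the faulty sentence sits where the matching window after study drug should be. At stake is the clarity of expedited safety reporting from the site to the Sponsor. No estimate or test is involved.

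**Working it through.** There is no statistical figure to reproduce. The check compares the sentence with the other sections under each reading it could bear.

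**1. Read as a deadline (when the report is sent).** The sentence allows reporting only after Follow-up. The 24-hour limit for SAEs or AESIs stands in 8.1.2, 8.1.3, 8.3.1, 8.4 and later in 8.4.2.2 itself. It recurs for particular cases in 8.3.1.3 (event becomes serious), 8.3.1.6 (liver cases), 8.3.1.7 (serious events from overdose or medication error), 8.4.1 (fatal or life-threatening), 8.4.2.1 (before study drug) and 8.4.2.3.2 (congenital anomaly). That is 5 + 6 = 11 places, against one sentence. This reading fails.

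**2. Read as a window (which events are reportable).** The sentence would cover only events occurring after Follow-up. Sections 8.2.1 and 8.6 define the reporting period as running up to Follow-up, and 4.1 has adverse events recorded over the same span. Section 8.4.2 would then give no window at all between first dose and Follow-up, which is the period that the heading of 8.4.2.2 announces. This reading fails.

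**3. Read as a special rule for events after Follow-up.** The provisions do not match:

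| | 8.4.2.2 | 8.2.1 and 8.6 |
|---|---|---|
| Condition | None on relatedness | Only events believed related to study drug |
| Route | Paper form to Covance PSS, with entry in the AE eCRF | AE eCRF; paper form only if the EDC system is unavailable (8.6) |
| Named recipient of the paper form | Covance PSS | Genentech United Kingdom Drug Safety (8.6) |

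The heading of 8.4.2.2 also covers everything after study drug initiation, not only the time after Follow-up. This reading fails too.

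**4. Size of the conflict under the first reading.** Inputs: three doses, at least 10 days between doses (4.1), Follow-up 12 to 14 days after the last dose (4.1).

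- First dose to last dose at minimum spacing: 2 × 10 = 20 days.
- First dose to Follow-up: 20 + 12 = 32 days to 20 + 14 = 34 days.
- Last dose to Follow-up: 12 to 14 days.

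A subject who completes all three periods and has an SAE on Period 1 Day 1 would, on the literal wording, be reported no earlier than 32 to 34 days later. An event just after the last dose would wait 12 to 14 days. The limit elsewhere is 1 day. Wider spacing between doses lengthens the first interval.

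**The case against.** The strongest reply is that this is a one-word drafting error with no demonstrated consequence. The 24-hour limit appears in 11 places, one of them in the same paragraph, and the parent section admits no exception. An Investigator could not delay a report on the strength of this sentence without disregarding both. The 32 to 34 days arise only on a literal reading that the rest of the paragraph overrides. No endpoint, PK analysis or adverse event count changes.

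Most of this stands. It is why the point is one of clarity and not evidence that reports would be late. Two further objections also have force. The mismatch in condition and route for events after Follow-up arises only if the sentence is taken literally, because 8.2.1 and 8.6 plainly govern those events. And 4.1, like the quoted sentence of 8.2.1, speaks of recording adverse events; the better support is the defined reporting period in 8.2.1 and 8.6.

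What does not follow is that the sentence can be left. It is current, operative text in the section to which the protocol directs the Investigator, and it is wrong on every reading. A safety-reporting instruction should not require its reader to infer which of two conflicting statements applies.

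**Conclusion.** The concern holds. The opening sentence of 8.4.2.2 contradicts the 24-hour instruction in its own paragraph, the unconditional limit in 8.4, and the reporting period defined in 8.2.1 and 8.6. It is most likely a slip of *after* for *until*; that is an inference from the surrounding sections, since the protocol does not say what was intended.

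One sentence is affected, and the remainder of 8.4.2.2 is sound. The consequence is an unclear reporting instruction at the site. The delay calculated above is an illustration that assumes the literal reading, all three doses given and minimum spacing; it is not an expected delay. The correction should be made, but nothing in the statistical analysis depends on it.

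**What to change.** Reconcile the opening sentence of 8.4.2.2 with 8.1.2, 8.1.3, 8.2.1, 8.4 and 8.6. It should state that SAEs and AESIs are reported from first dose until Follow-up (12 to 14 days after the final dose), within the 24-hour limit the section already contains. For events after Follow-up, add a reference to 8.6 and to 8.2.1, which also names AESIs, so that their relatedness condition and route apply.

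This introduces no new rule. The cost is one sentence in the next protocol amendment or in a clarification letter to the site, with no change to procedures, data collection, the SAP or the analysis.

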8.4.2.3 REPORTING REQUIREMENTS FOR PREGNANCIES

8.4.2.3.1 PREGNANCIES IN FEMALE SUBJECTS

Female subjects will be instructed to immediately inform the Investigator if they become pregnant during the study or within 90 days after the final dose of study drug. A paper Clinical Trial Pregnancy Reporting Form should be completed by the Investigator immediately (i.e., no more than 24 hours after learning of the pregnancy) and emailed to Covance PSS (see [Section 8.4.2](#) for reporting instructions). Pregnancy should not be recorded on the AE eCRF. The Investigator should discontinue study drug and counsel the subject, discussing the risks of the pregnancy and the possible effects on the fetus. Monitoring of the subject should continue until conclusion of the pregnancy. Any SAEs associated with the pregnancy (e.g., an event in the fetus, an event in the mother during or after the pregnancy, or a congenital anomaly/birth defect in the child) should be reported on the AE eCRF. In addition, the Investigator will submit a paper Clinical Trial Pregnancy Reporting Form when updated information on the course and outcome of the pregnancy becomes available.

8.4.2.3.2 CONGENITAL ANOMALIES/BIRTH DEFECTS AND ABORTIONS

Any congenital anomaly/birth defect in a child born to a female subject exposed to the study drug should be classified as an SAE, recorded on the AE eCRF, and reported to the Sponsor immediately via Covance PSS (i.e., no more than 24 hours after learning of the event; see [Section 8.4.2](#)). Any abortion should be reported in the same fashion (as the Sponsor considers abortions to be medically significant events). All abortions should be reported as pregnancy outcomes on the paper Clinical Trial Pregnancy Reporting Form.

8.5 FOLLOW-UP OF SUBJECTS AFTER ADVERSE EVENTS

8.5.1 INVESTIGATOR FOLLOW-UP

The Investigator should follow each AE until the event has resolved to baseline grade or better, the event is assessed as stable by the Investigator, the subject is lost to follow-up, or the subject withdraws consent. Every effort should be made to follow all SAEs considered to be related to study drug or trial-related procedures until a final outcome can be reported. During the study period, resolution of AEs (with dates) should be documented on the AE eCRF and in the subject's medical record to facilitate source data verification.

All pregnancies reported during the study should be followed until pregnancy outcome.

8.5.2 SPONSOR FOLLOW-UP

For SAEs, AESIs, and pregnancies, the Sponsor or a designee may follow-up by telephone, fax, email, and/or a monitoring visit to obtain additional case details and outcome information (e.g., from hospital discharge summaries, consultant reports, autopsy reports) in order to perform an independent medical assessment of the reported case.

8.6 ADVERSE EVENTS THAT OCCUR AFTER THE ADVERSE EVENT REPORTING PERIOD

At the Follow-up/ET visit, the Investigator should instruct each subject to report to the Investigator any subsequent AEs that the subject's personal physician believes could be related to prior study drug treatment or study procedures. The Sponsor should be notified if the Investigator becomes aware of any SAE that occurs after the end of the AE reporting period (defined as until Follow-up, 12 to 14 days after the final dose of study drug) if the event is believed to be related to prior study drug treatment.

These events should be reported through the use of the AE eCRF. However, if the EDC system is not available, the Investigator should report these events directly to the Sponsor or its designee, by faxing or by scanning and emailing the paper Clinical Trial SAE/AESI Reporting Form using the below fax number or email address provided to Investigators.

Genentech United Kingdom Drug Safety

Email Address: [contact]

[contact]

8.6.1 EXPEDITED REPORTING TO HEALTH AUTHORITIES, INVESTIGATORS, INSTITUTIONAL REVIEW BOARDS, AND ETHICS COMMITTEES

The Sponsor will promptly evaluate all SAEs and AESIs against cumulative product experience to identify and expeditiously communicate possible new safety findings to Investigators, IRBs, ECs, and applicable health authorities based on applicable legislation.

To determine reporting requirements for single AE cases, the Sponsor will assess the expectedness of these events using the following reference document(s):

- GDC-9545 IB

The Sponsor will compare the severity of each event and the cumulative event frequency reported for the study with the severity and frequency reported in the applicable reference document.

Reporting requirements will also be based on the Investigator's assessment of causality and seriousness, with allowance for upgrading by the Sponsor as needed.

The IRB will be notified by the investigative site in writing (e.g., email) within the timeframe required per local IRB regulations when a reportable AE is first recognized or reported. In addition, a copy of the written confirmation or summary of the AE, as submitted to the Sponsor, will also be submitted to the IRB within that same timeframe from when the AE is first recognized or reported. The IRB Serious and Unexpected AE Submission Form will be completed and submitted with the copy of the written confirmation or summary of the AE.

9 STATISTICAL ANALYSES

The Safety Population will consist of all subjects who received at least one dose of study drug.

The PK Population will consist of all subjects who received at least one dose of study drug and have at least one evaluable postdose PK sample.

Baseline is defined as the last result prior to the first dose of study drug on Period 1 Day 1. As necessary, baseline will be further defined in the Statistical Analysis Plan (SAP).

9.1 SAFETY AND TOLERABILITY ANALYSIS

Safety will be assessed by a review of AEs, clinical laboratory assessments, vital signs, and ECGs. Clinical laboratory assessments, vital signs (including oral temperature, respiratory rate, and supine blood pressure and pulse), and ECGs will be listed by subject number and scheduled time, and changes from baseline will be summarized.

Verbatim descriptions of AEs will be coded according to current Medical Dictionary for Regulatory Activities version 22.0 (or higher) guidelines. Adverse events will be summarized. Enrollment and discontinuations from the study will be summarized overall. Demographics and baseline characteristics such as age, sex, and BMI will be summarized overall.

